9.7 Power for the key secondary hypotheses

Not applicable.

9.9 Interim analysis

Not applicable. No interim analysis is planned for this study.

10 Ethical considerations

10.1 Regulatory and ethical compliance

This clinical study was designed and shall be implemented and reported in accordance with the ICH Harmonized tripartite guidelines for Good Clinical Practice, with applicable local regulations (including European Directive 2001/20/EC, US Code of Federal Regulations Title 21, and Japanese Ministry of Health, Labor, and Welfare), and with the ethical principles laid down in the Declaration of Helsinki.

10.2 Informed consent procedures

Eligible patients may only be included in the study after providing written (witnessed, where required by law or regulation), IRB/IEC-approved informed consent, or, if incapable of doing so, after such consent has been provided by a legally acceptable representative of the patient. In cases where the patient's representative gives consent, the patient should be informed about the study to the extent possible given his or her understanding. If the patient is capable of doing so, he or she should indicate assent by personally signing and dating the written informed consent document or a separate assent form. Informed consent must be obtained before conducting any study-specific procedures (i.e., all of the procedures described in the protocol). The process of obtaining informed consent should be documented in the patient's source documents.

will provide to investigators in a separate document a proposed informed consent form that complies with the ICH Good Clinical Practice guideline and regulatory requirements and is considered appropriate for this study. Any changes to the proposed consent form suggested by the investigator must be agreed to by before submission to the IRB/IEC, and a copy of the approved version must be provided to the monitor after IRB/IEC approval.

10.3 Responsibilities of the investigator and IRB/IEC

The protocol and the proposed informed consent form must be reviewed and approved by a properly constituted IRB/IEC before study start. A signed and dated statement that the protocol and informed consent have been approved by the IRB/IEC must be given to Novartis/ before study initiation. Before study start, the investigator is required to sign a protocol signature page confirming his/her agreement to conduct the study in accordance with these documents and all of the instructions and procedures found in this protocol and to give access to all relevant data and records to Novartis/ monitors, auditors, Novartis/ IRBs/IECs, and regulatory authorities as required. If an inspection of the clinical site is requested by a regulatory authority, the investigator must inform Novartis immediately that this request has been made.

10.4 Publication of study protocol and results

Novartis assures that the key design elements of this protocol will be posted in a publicly accessible database such as clinicaltrials.gov. In addition, upon study completion and finalization of the study report the results of this trial will be either submitted for publication and/or posted in a publicly accessible database of clinical trial results.

11 Protocol adherence

Investigators agree that they will apply due diligence to avoid protocol deviations. Under no circumstances should the investigator contact Novartis or its agents, if any, monitoring the trial to request approval of a protocol deviation as no authorized deviations are permitted. If the investigator feels that a protocol deviation would improve the conduct of the study, this must be considered a protocol amendment. Unless such an amendment is agreed upon by Novartis and approved by the IRB/IEC, it cannot be implemented. All significant protocol deviations will be recorded and reported in the clinical study report.

Appendix 1: Clinically notable laboratory values and vital signs

Only selected lab parameters identified as notable which have been shown to be sensitive to fingolimod exposure are included.

CRITERIA FOR NOTABLE LABORATORY ABNORMALITIES

Notable Values		
Laboratory Variable	Standard Units	SI Units
LIVER FUNCTION AND F	RELATED VARIABLES	
SGOT (AST)	>82 U/L	>82 U/L
SGPT (ALT)	>90 U/L	>90 U/L
Total bilirubin	≥2.0 mg/dL	≥34.2 μmol/L
Alkaline phosphatase	>280 U/L	>280 U/L
RENAL FUNCTION / ME	TABOLIC AND ELECTRO	LYTE VARIABLES
Glucose `	≥200 mg/dL	≥11.11 mmol/L
Creatinine	≥2.0 mg/dL	≥176 umol/L
Amylase	≥300 U/L	≥300 U/L
Cholesterol	≥240 mg/dL	≥6.21 mmol/L
Triglycerides	≥300 mg/dL	≥3.39 mmol/L
Blood urea nitrogen (BUN)	≤2 mg/dL	≤0.7 mmol/L
	≥30 mg/dL	≥10.7 mmol/L
Sodium	<125 mEq/L	<125 mmol/L
	>154 mEq/L	>154 mmol/L
Chloride	≤85 mEq/L	≤85 mmol/L
	≥119mEq/L	≥119 mmol/L
Potassium	≤3.0 mEq/L	≤3.0 mmol/L
	≥6.0 mEq/L	≥6.0 mmol/L
Magnesium	≤1.0 mg/dL	≤0.40 mmol/L
	≥3.0 mg/dL	≥1.23 mmol/L
Calcium	≤7.5 mg/dL	≤1.87 mmol/L
	≥11.6 mg/dL	≥2.89 mmol/L
Phosphate	≤2.0 mg/dL	≤0.65 mmol/L
	≥5.3 mg/dL	≥1.71 mmol/L

Notable Values				
Laboratory Variable	Standard Units	SI Units		
HEMATOLOGY VARIABLES	S			
Hemoglobin	≤10.0 g/dL (M/F)	≤100 g/L (M/F)		
Platelets (Thrombocytes)	≤100 k/mm ³	≤100 x 10 ⁹ /L		
	≥600 k/mm ³	≥600 x 10 ⁹ /L		
Leukocytes (WBCs)	≤2.0 k/mm ³	≤2.0 x 10 ⁹ /L		
	≥15 k/mm³	≥15 x 10 ⁹ /L		
HEMATOLOGY VARIABLES	S: DIFFERENTIAL			
Granulocytes (Poly, Neutrophils)	≤1,000 /mm³	≤1 x 10 ⁹ /L		
	≥12000/mm ³	≥12 x 10 ⁹ /L		
Lymphocytes	<200/mm ³	<0.2 x 10 ⁹ /L		
	≥8000/mm ³	≥8 x 10 ⁹ /L		
Red blood cells	<3,300,000/mm ³	<3.3 x 10 ¹² /L		
	>6,800,000/mm ³	>6.8 x 10 ¹² /L		

NOTABLE VITAL SIGNS AND BODY WEIGHT			
Vital Sign Variable	Notable Criteria		
Pulse (beats/min)	>120 bpm or Increase of ≥15 bpm from baseline		
	Or		
	<50 bpm or Decrease of ≥15 bpm from baseline		
Systolic BP (mm Hg)	≥160 mm Hg or Increase of ≥20 mm Hg from baseline		
	Or		
	≤90 mm Hg or Decrease of ≥20 mm Hg from baseline		
Diastolic BP (mm Hg)	≥100 mm Hg or Increase of ≥15 mm Hg from baseline		
	Or		
	≤50 mm Hg or Decrease of ≥15 mm Hg from baseline		
Body Temperature (°C)	>38.3°C/101°F		
Body Weight (kg)	± 7% from baseline weight		

Appendix 2: 2010 Revisions to the McDonald diagnosis criteria for MS

Guidelines from International Panel on the diagnosis of MS

(McDonald et al, 2001; Polman et al, 2005; Polman et al, 2011)

Clinical Presentation	Additional Data Needed for MS Diagnosis
2 or more attacks ^a ; objective	None ^c
clinical evidence of 2 or more	
lesions or objective clinical	
evidence of 1 lesion with	
reasonable historical evidence	
of a prior attack ^b	
Two or more attacks ^a ; objective clinical	Dissemination in space , demonstrated by:
evidence of 1 lesion	≥1 T2 lesion in at least two out of four MS-typical regions of the CNS (periventricular, juxtacortical, infratentorial, or spinal cord) ^d
	OR
	Await a further clinical attack ^a implicating a different CNS site
One attack ^a ; objective clinical evidence of 2 of	or Dissemination in time , demonstrated by:
more lesions	Simultaneous presence of asymptomatic gadolinium-enhancing and non-enhancing lesions at any time.
	OR
	A new T2 and/or gadolinium-enhancing lesion(s) on follow-up MRI, irrespective of its timing with reference to a baseline scan.
	OR
	Await a further clinical attack ^a

One attack^a; objective clinical evidence of 1 lesion (clinically isolated syndrome)

Dissemination in space and time, demonstrated by:

For DIS

≥1 T2 lesion in at least two out of four MS-typical regions of the CNS periventricular, juxtacortical, infratentorial, or spinal cord)^d

OR

Await a second clinical attack^a implicating a different CNS site

AND

For DIT

Simultaneous presence of asymptomatic gadolinium-enhancing and non-enhancing lesions at any time.

OR

A new T2 and/or gadolinium-enhancing lesion(s) on follow-up MRI, irrespective of its timing with reference to a baseline scan.

OR

Await a second clinical attack^a

If the Criteria are fulfilled the diagnosis is MS.

^a·An attack (relapse; exacerbation) is defined this as patient-reported or objectively observed events typical of an acute inflammatory demyelinating event in the CNS, current or historical, with duration of at least 24 hours, in the absence of fever or infection. It should be documented by contemporaneous neurological examination, but some historical events with symptoms and evolution characteristic for MS, but for which no objective neurological findings are documented, can provide reasonable evidence of a prior demyelinating event. Reports of paroxysmal symptoms (historical or current) should, however, consist of multiple episodes occurring over not less than 24 hours. Before a definite diagnosis of MS can be made, at least one attack must be corroborated by findings on neurological examination, visual evoked potential (VEP) response in patients reporting prior visual disturbance, or MRI consistent with demyelination in the area of the CNS implicated in the historical report of neurological symptoms.

^bClinical diagnosis based on objective clinical findings for two attacks is most secure. Reasonable historical evidence for one past attack, in the absence of documented objective neurological findings, can include historical events with symptoms and evolution characteristics for a prior inflammatory demyelinating event; at least one attack, however, must be supported by objective findings.

^cNo additional tests are required. However, it is desirable that any diagnosis of MS be made with access to imaging based on these Criteria. If imaging or other tests (for instance, CSF) are undertaken and are NEGATIVE, extreme caution needs to be taken before making a diagnosis of MS and alternative diagnoses must be considered. There must be no better explanation for the clinical presentation and objective evidence must be present to support a diagnosis of MS.

^dGadolinium-enhancing lesions are not required; symptomatic lesions are excluded from consideration in subjects with brainstem or spinal cord syndromes.

Appendix 3: Guidance on safety monitoring

Patients whose blood pressure reading is \geq 140 (systolic) and/or \geq 90 mm Hg (diastolic) should have their blood pressure retested after 15 minutes of rest. If the blood pressure is still elevated, they should be followed up in one month by an unscheduled visit if the scheduled visit is not due. Should systolic BP \geq 140 and/or diastolic BP \geq 90 mm Hg values be confirmed at the second visit, the patient should be referred to his primary care physician, an independent internist or to the specialty hypertension clinic for evaluation, diagnosis and treatment of hypertension.

Patients with BP values of >160/100 mm Hg (confirmed by repeat testing) at any visit during the study should be immediately referred as above for evaluation, diagnosis and treatment of hypertension.

Newly diagnosed hypertension as well as an aggravation of a preexisting condition must be reported as an AE and appropriate antihypertensive medication/dosage adjustment must be considered by the investigator.

Guidance on monitoring of patients with elevated liver function tests

In case of detection of elevated ALT/AST values >2 and <5 times the ULN range, additional blood chemistry panel including ALT, AST, AP, GGT, total and conjugated bilirubin, albumin may be performed at the investigator's discretion.

If ALT/AST values reach 5 times the ULN, confirmed upon repeat testing within two weeks of the initial result or sooner at the discretion of the investigator, the study drug must be permanently discontinued. Patients who develop symptoms suggestive of hepatic dysfunction such as unexplained vomiting or jaundice, should have liver enzymes checked and fingolimod should be discontinued if significant liver injury is confirmed.

In case of isolated elevation of bilirubin over 2.0 mg/dl (34.2 umol/L) unless in context of Gilbert's syndrome, confirmed upon repeat testing within two weeks of the initial result, the investigator must discontinue the study drug. Additional evaluations may be performed at the discretion of the investigator.

For any unscheduled laboratory assessments performed locally, an identical sample should also be sent to the central laboratory for analysis and capture in the central database.

An interruption or discontinuation of the study drug should be clearly documented and reflected on Dosage Administration Record CRF. AE/SAEs need to be filed as appropriate.

Guidance on monitoring of patients with notable lymphopenia

Fingolimod results in sequestration of a proportion of the circulating lymphocytes in lymph nodes with resultant reduction in circulating lymphocyte counts. Average circulating lymphocytes counts are expected to be around 0.5 -0.6 x10⁹/L or 500- 600 cells/mm³. Please see Investigator Brochure for more details. As such, the absolute total WBC, neutrophil and lymphocyte counts will be measured at each visit by the central laboratory, but will be reported blinded for subjects randomized to fingolimod. Lymphocyte counts below 0.2x10⁹/L in patients randomized to fingolimod treatment are reported unblinded and require repeat

testing within 2 weeks. If the repeat test confirms lymphocyte counts below $0.2x10^9/L$, the investigator should perform at least monthly retests. Results will only be reported blinded again once they reach $0.6x10^9/L$.

If the repeat test confirms the lymphocyte count is below $0.2x10^9/L$ or 200 cells/mm³ and there are no signs or symptoms of infection, the patient can continue on study medication at the discretion of the investigator with regular monitoring for signs of infections.

If the patient presents with signs of infection and the lymphocyte count is below $0.2x10^9/L$, the study drug must be temporarily interrupted, and the investigator should consider treatment with a specific therapy on the basis of the clinical diagnosis in consultation with an infectious disease specialist. Reinitiation of the study drug can only be considered once the lymphocyte count reaches 600 cells/mm³ as confirmed by the central laboratory and after discussion with the Medical Monitor.

If the patient is randomized to the glatiramer acetate treatment group and presents with significant lymphopenia (<50% baseline) confirmed on repeat test by central laboratory within two weeks, study drug must be interrupted and further diagnostic work-up needs to be initiated. The investigator should only consider re-initiation of the glatiramer acetate after a thorough diagnostic workup has been performed, diagnosis/cause for the lymphopenia has been established, treatment has been initiated as adequate, and only after discussion with Medical Monitor and if the patient shows no signs or symptoms of infection or malignancy.

Guidance on monitoring of patients with symptoms of neurological deterioration, inconsistent with MS course

Should a patient develop any manifestations that, in opinion of the investigator, are atypical for multiple sclerosis including unexpected neurological or psychiatric symptom/signs (e.g. rapid cognitive decline, behavioral changes, cortical visual disturbances or any other neurological cortical symptoms/sign), or any symptom/sign suggestive of an increase of intracranial pressure or accelerated neurological deterioration, the investigator should schedule a complete physical and neurological examination and an MRI as soon as possible and before beginning any steroid treatment. Conventional MRI as defined in the protocol as well as Fluid-attenuated Inversion Recovery (FLAIR) and Diffusion-weighted imaging (DWI) sequences are recommended for differential diagnosis of Posterior reversible encephalopathy syndrome. The MRI must be evaluated by the local neuroradiologist. The investigator will contact the Medical Advisor at Novartis to discuss findings and diagnostic possibilities as soon as possible. AE/SAEs need to be filed as appropriate.

In case of new findings in the MRI images in comparison with the previous available MRI which are not compatible with MS lesions, the study drug will be discontinued and other diagnostic evaluations need to be performed at the discretion of the investigator. In case of presence of new hyperintense T2-weighted lesions in the MRI which may be infectious in origin it is recommended to collect a cerebrospinal fluid sample if indicated. Analysis of the CSF sample including cellular, biochemical and, microbiological analysis (e.g. herpes virus, JC virus), to confirm/exclude an infection (e.g. PML) should be performed. In the event of suspected CNS infection, a CSF aliquot should be sent to a central laboratory (designated by the sponsor) for confirmatory testing.

Only when the differential diagnosis evaluations have excluded other possible diagnosis than MS and after discussion with the Medical Advisor at Novartis, the study drug may be restarted.

Guidance on monitoring of patients with infections

All infections that develop during the study will be reported as AEs. Investigators are requested to specifically ask about infections at each visit. Treatment and additional evaluations will be performed at discretion of the investigator.

The investigator should be vigilant for risk of infections including opportunistic infections due to bacterial infections (e.g., atypical mycobacteria), viral infections (e.g., HSV, VZV, JCV), or fungal infections (e.g., cryptococcus agents) and should remind the patient of the risk of infections and to instruct them to promptly report any symptoms of infections to the investigator. The patients must also be reminded to always carry their Patient Information Card (with site contact information and which identifies them as participants in a clinical study with an agent with potential immunosuppressive effects) and to show this to any local healthcare provider they may consult and ask that the investigator be contacted.

When evaluating a patient with a suspected infection, the most sensitive tests available should be used (i.e. that directly detect the pathogen, as with PCR).

The investigator should consider early treatment with specific therapy on the basis of clinical diagnosis or suspicion thereof (e.g., antiviral treatment for herpes simplex or VZV; treatment for cryptococcus) in consultation with infectious disease experts, as appropriate. Investigators should be aware that in the post-marketing setting with fingolimod, isolated cases of cryptococcal meningitis have been reported. Patients reporting symptoms and signs (such as, but not limited to, headache accompanied with stiff neck, sensitivity to light, fever, confusion, tiredness, body aches, chills, vomiting, and/or nausea) consistent with meningitis should undergo prompt diagnostic evaluation. If (cryptococcal) meningitis is diagnosed, appropriate antibiotic treatment should be initiated as soon as possible. The investigator should inform the Novartis medical expert and the CRO's medical expert of any such cases.

Suspension of treatment with fingolimod should be considered if a patient develops a serious infection, and consideration of benefit-risk should be undertaken prior to re-initiation of therapy.

Investigators should consider the added immunosuppressive effects of corticosteroid therapy for treatment of MS attack/relapse and increase vigilance regarding infections during such therapy and in the weeks following administration.

Patients should be evaluated for evidence of immunity to VZV based on any of the following:

- Laboratory evidence of immunity or laboratory confirmation of disease
- Diagnosis or verification of a history of VZV or herpes zoster by a health care provider

To verify a history of VZV, health care providers should inquire about:

- An epidemiologic link to another typical VZV case or to a laboratory confirmed case,
- Evidence of laboratory confirmation, if testing was performed at the time of acute disease

The VZV vaccination of antibody-negative patients should be considered prior to commencing treatment with fingolimod, following which initiation of study drug should be postponed for at least 1 month to allow full effect of vaccination to occur.

Serology testing for antibody status of HSV-1 and HSV-2 and rubeola (measles) is performed at screening to profile infection risk in study patients. The investigator should inform the patients of their immune status based on these serology results and of the potential risks of primary infections or viral reactivation while taking fingolimod.

A positive IgG antibody test result does not indicate active infection per se, but only evidence of exposure to viral antigens via past infection or vaccination. These patients may however, be at risk for viral reactivation, which may manifest as:

- VZV virus IgG positive: Shingles
- HSV-1 IgG positive: Cold sores
- HSV-2 IgG positive: Herpes genitalis

The investigator should instruct the patient to be alert to and report any symptoms or signs suggestive of cold sores, genital ulcers or shingles, so that appropriate anti-viral treatment can be initiated in consultation with a local infectious disease expert (if needed).

A negative IgG antibody test result for HSV-1, HSV-2, and rubeola places patients at risk for more severe and atypical manifestations of primary infection in the event they are exposed to these viruses while they are immunosuppressed (taking study drug and/or corticosteroids).

Patients who are negative for HSV-1 IgG, HSV-2 IgG and rubeola antibodies should be instructed to promptly report any exposure to these viruses i.e. to a person with cold sores, herpes genitalis, respectively. In case of exposure, early treatment with appropriate antiviral drugs should be considered in consultation with a local infectious diseases expert.

It is also important to ask the patient receiving fingolimod to report if they are exposed to anyone who has recently received a live or live attenuated vaccine and manifested a skin rash after the vaccination so that it can be decided, in consultation with an infectious disease expert, if antiviral therapy is warranted.

It should be noted that live or live attenuated vaccines are prohibited while fingolimod patients are taking study drug and for 8 weeks after study drug discontinuation.

Guidance on monitoring pulmonary function

Patients reporting any respiratory symptoms such as dyspnea, shortness of breath, chest tightness, wheezing should be seen at an unscheduled visit for clinical assessment. A full pulmonary function test (FEV₁, FVC, and D_LCO_c [i.e., D_LCO_c and a bronchodilator reversibility test need to be performed, preferably on the same day. If PFTs demonstrate reduction of FEV₁ or FVC values to 80% or below of baseline values, initiation of treatment with bronchodilators will be considered.

In case of reduction of FEV₁, FVC, and/or D_LCO_c below 80% of baseline values, the patient's pulmonary status will require a follow-up as soon as possible within no more than 1 month, including history of respiratory symptoms (eg, dyspnea, shortness of breath, chest tightness, wheezing), physical examination, FEV₁, FVC, D_LCO_c measurement, and a bronchodilator reversibility test.

Should repeat PFT values (FEV₁, FVC, and/or D_LCO_c) remain below 80% of baseline values or should a worsening of the previously reported respiratory symptoms be observed, the patient will be referred to pneumologist (pulmonologist) for further evaluation, including chest HRCT and treatment. A standard referral letter explaining a reason for referral should be accompanied by the sponsor's information letter about the investigational drug (FTY720).

In case of reduction of FEV₁, FVC, and/or D_LCO_c below 60% of baseline value in any visit, the study drug should be discontinued and the patient must be immediately referred to pneumologist (pulmonologist) for further evaluation, including chest HRCT and treatment.

In case of persistent reduction of FEV₁, FVC, and/or D_LCO_c below 80% over 3-month period despite appropriate treatment, the Primary Treating Physician should consider an interruption of the study drug. This decision may be discussed with Medical Monitor.

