The requirement for serology testing of hepatitis A, B, C, and E, at Screening was omitted. This criterion (exclusion criterion 8 in protocol amendment version 1) has been modified to be in alignment with the current US prescribing information and the prescribing information in other countries which are within the scope of this study which does not require such screening before initiating treatment with fingolimod in clinical practice. The liver functions are being tested very closely at Screening, Baseline, and periodically during the study to capture any

instances of liver infections/impairment (if any) early and are considered as adequate safeguards.

The current exclusion criterion 8 regarding mandatory serologic screening for antibodies against varicella zoster virus (VZV) is a modification which also allows for alternative acceptable evidence of immunity (as per Center for Disease Control guidance). This brings the protocol in alignment with the guidance in the current US prescribing information in this context.

The current exclusion criteria 12, 13, and 14 have modified text to align with the US prescribing information and the prescribing information in other countries which are within the scope of this study. The exclusion clauses in protocol amendment version 1 were more restrictive than that recommended in the US prescribing information resulting in exclusion of those patients with certain pre-existing cardiac conditions or on concomitant drugs prolonging heart rate or atrioventricular (AV) conduction, who would have been otherwise eligible to initiate fingolimod with extended monitoring.

Certain clarifications and corrections were also done in the protocol as follows:

The exclusion criterion 16 provides clarification that patients with controlled asthma are allowed to participate in the study.

The prohibition period for the administration of a live or live-attenuated vaccine after fingolimod discontinuation was corrected from 12 to 8 weeks (as per US prescribing information).

Clarification was provided that the patients known to be allergic to gadolinium (Gd) may participate in the trial with magnetic resonance imaging (MRI) performance modified only to forgo contrasted MRI images.

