6.5.3 Laboratory evaluations

Routine blood samples will be collected as described in Table 6-1 and Table 6-2 and analyzed by the central laboratory. Blood samples taken at the screening visit are to be in the fasting state. Blood samples taken at subsequent visits are recommended to be in the fasting state. Details regarding collection of samples, shipment of samples, reporting of results, laboratory reference ranges, and alerting abnormal values will be supplied to the site before site initiation in a study laboratory manual. The results of the analysis will be made available to each site by the central laboratory, at the earliest, 48 hours after receipt of the samples by the central laboratory.

Investigators will be asked to comment on those abnormalities on the respective laboratory result page, including a notation of the clinical significance of each abnormal finding in the patient's source documents. The laboratory sheets will be filed with the patient's source documents. Abnormal laboratory values should not be recorded on the AE eCRF; however,

any diagnoses (or signs or symptoms if a diagnosis is not possible) associated with the abnormal findings should be recorded on the AE eCRF.

Clinically notable laboratory findings are defined in Appendix 1.

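### Appendix 3 makes a confirmed 'isolated' bilirubin over 2.0 mg/dL a mandatory stop but, read literally, does not require one when ALT/AST is also raised and below 5 x ULN

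*Protocol*

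**What the plan says.** The rules are in Protocol Appendix 3, under the guidance on elevated liver function tests.

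- **Middle ALT/AST tier.** "In case of detection of elevated ALT/AST values >2 and <5 times the ULN range", an "additional blood chemistry panel including ALT, AST, AP, GGT, total and conjugated bilirubin, albumin may be performed at the investigator's discretion". No stop is attached to this tier.
- **ALT/AST stop.** "If ALT/AST values reach 5 times the ULN, confirmed upon repeat testing within two weeks of the initial result" (or sooner), study drug must be stopped permanently.
- **Bilirubin stop.** "In case of isolated elevation of bilirubin over 2.0 mg/dl (34.2 umol/L) unless in context of Gilbert's syndrome, confirmed upon repeat testing within two weeks": the investigator must stop study drug.
- **Symptom clause.** Patients with symptoms such as unexplained vomiting or jaundice should have liver enzymes checked, and "fingolimod should be discontinued if significant liver injury is confirmed".

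The Amendment 02 rationale, explaining why screening serology for hepatitis A, B, C and E was dropped, says: "The liver functions are being tested very closely at Screening, Baseline, and periodically during the study". It counts this testing as an adequate safeguard against liver infection or impairment.

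**The concern.** Raised bilirubin together with raised transaminases is a more worrying picture than raised bilirubin alone, and one would expect the instruction to be at least as strong. The word 'isolated' makes it weaker on a literal reading: it limits the mandatory bilirubin stop to patients whose other liver values are, presumably, not raised.

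Participant safety and consistent handling across sites are at stake. Protocol Section 1.1 names liver enzyme elevation among the adverse events most prominently associated with fingolimod and says that these appeared dose-related. Since Amendment 02 relies on liver function tests in place of hepatitis serology, what an abnormal test triggers should be unambiguous. As written, whether a patient in the combined range stays on study drug is left to each investigator's judgment.

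**Working it through.** No power, sample size or error rate is involved, so the check is a decision table. Take a bilirubin above 2.0 mg/dL, confirmed on repeat, in a patient without Gilbert's syndrome, and apply the Appendix 3 laboratory rules literally at each ALT/AST level.

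| ALT/AST | Bilirubin rule | ALT/AST rule | Mandatory stop? |
|---|---|---|---|
| Normal | Applies (isolated) | None | Yes |
| Above 1 and up to 2 x ULN | Unclear: 'isolated' undefined | None | Unclear |
| Above 2 and below 5 x ULN | Does not apply (not isolated) | Optional panel | No |
| 5 x ULN or above, confirmed | Not needed | Permanent stop | Yes |

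A mandatory stop therefore exists on both sides of the combined range and is missing inside it.

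The next step is to see whether another provision supplies the missing requirement.

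- **Symptom clause, Appendix 3.** It is worded as 'should', depends on symptoms, leaves significant liver injury undefined, and names only fingolimod.
- **Protocol 5.5.6.** Abnormal laboratory values may lead to interruption on the investigator's judgment; for detail it refers back to Appendix 3.
- **Protocol Appendix 1.** Bilirubin at or above 2.0 mg/dL, ALT above 90 U/L and AST above 82 U/L are listed as notable. The appendix describes its content thus: "Only selected lab parameters identified as notable which have been shown to be sensitive to fingolimod exposure are included". It attaches no liver action.
- **Protocol 6.5.3 and 6.5.3.2.** "Investigators will be asked to comment on those abnormalities on the respective laboratory result page", and suspicious values should be repeated. Neither requires a stop.
- **Protocol 7.1, 7.2 and 7.4.** Clinically significant values are adverse events followed to resolution, with permanent discontinuation one possible action. Serious events go to the sponsor within 24 hours. The safety board reviews events of interest. These are reporting and oversight routes.
- **SAP 8.2.2.** The modified Hy's Law criterion (ALT or AST above 3 x ULN, total bilirubin at least 2 x ULN and alkaline phosphatase below 2 x ULN at the same visit) identifies patients for a summary table.
- **Protocol 4.2, criterion 17.** Its limits of 2 x ULN for ALT/AST and for bilirubin apply at entry only.

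None requires a stop for the combined case below 5 x ULN.

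The lymphopenia guidance in the same appendix is a useful comparison. A confirmed lymphocyte count below 0.2 x 10^9/L without infection leaves continuation to the investigator; a count below that limit with signs of infection makes interruption mandatory. There a second abnormality strengthens the instruction. In the liver text, read literally, it weakens it.

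**The case against.** The strongest reply is about meaning. 'Isolated' can be read as saying that bilirubin alone is enough. On that reading a raised ALT cannot cancel a mandatory bilirubin stop, the combined case is covered all the more, and there is no gap. Nothing in the documents shows that any site read it otherwise. This reading is plausible and lowers the weight of the point. It does not remove it, because the text does not say so and a mandatory safety rule should not depend on inferring intent.

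The second reply is that the practical gap is narrow. Notable-value listing, repeat testing, investigator-judged interruption, the jaundice clause and adverse event or serious adverse event reporting all draw attention to such a patient, and serious cases reach the sponsor quickly. This also stands: many investigators would probably stop the drug. What these provisions do not do is require it.

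Two stronger readings are tempting, and the documents support neither. A reader might infer that the protocol tells sites to keep such patients on drug; it does not, since stopping is always permitted. A reader might also infer that the patient goes unexamined until the next scheduled chemistry. The case concerns a confirmed bilirubin, so the repeat within two weeks has already been done, and the prompts above still apply. The defect is a missing requirement to stop, not a delay in testing.

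**Conclusion.** The point holds as a literal-reading gap in a stated safety rule. It covers confirmed bilirubin over 2.0 mg/dL, outside Gilbert's syndrome, with ALT/AST above 2 and below 5 x ULN. Between 1 and 2 x ULN it is uncertain, because 'isolated' is undefined. Combined cases with confirmed ALT/AST at or above 5 x ULN are already covered, so it would be wrong to infer that all combined elevations escape a mandatory stop.

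The size cannot be expressed as a number of patients: the documents give no frequency for this combination and none is assumed here. Nor do they support reading this as a threat to the efficacy result. Under Protocol 5.5.10 and 9.4.3, patients who stop study drug stay in the study and their relapses count on or off drug, so the primary analysis is little affected either way.

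The conclusion rests on taking 'isolated' at face value. If the sponsor meant that bilirubin alone suffices, only an ambiguity remains. On either view it is a cheap improvement for patient safety.

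**What to change.** In the bilirubin paragraph of Appendix 3, delete 'isolated' and, straight after the threshold and its SI equivalent, insert 'with or without ALT/AST elevation'. Keep the Gilbert's exception, the two-week confirmation and the obligation to stop study drug. The rule then covers every confirmed case over 2.0 mg/dL outside Gilbert's syndrome, whatever the ALT/AST value.

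As a minor secondary edit, change 'fingolimod' to 'study drug' in the symptom clause. The glossary defines study drug to include control drugs, so this brings glatiramer acetate within the clause, as it already is for the two laboratory stops.

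The cost is one phrase, one term and a letter to sites. No tests are added, since ALT, AST and bilirubin are already part of the chemistry panel at Months 1, 3, 6, 9 and 12. The downside is possibly a few more study drug discontinuations, with those patients still followed for relapse. If combined cases were always meant to stop, the intended handling of patients does not change.
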